6.3 Analysis methods

6.3.1 Primary analysis

The primary analysis is based on the treatment policy estimand, using the full analysis set according to the intention to treat principle.

The primary outcome will be presented as proportion with 95% Wilson confidence interval in each intervention group and compared between groups using the chi-square test. The effect size will be presented as relative risk with 95% Koopman confidence interval, as well as risk difference with 95% Newcombe-hybrid-score confidence interval.

Secondary smoking outcomes will be analysed as the primary outcome.

Continuous secondary outcomes will be analysed using linear models, adjusted for the outcome measure at baseline, if it is available. Missing values in continuous outcomes will be imputed. Thus, the estimates of the complete data models are averaged using Rubin's rule (Rubin 1987). Effect sizes will be presented as mean difference with 95% confidence interval.

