9.3.2 Visit 1, Baseline visit at -7 days to target quit date

- Patient information and delivery of written study information to subject
- Verification of eligibility, including urine pregnancy test for premenopausal women
- Informed consent
- Demographics
- Relevant medical history including current medication
- Smoking history and symptoms linked to smoking, cigarette dependence (Fagerström Test for Cigarette Dependence), withdrawal symptoms
- Body weight, height, calculation of BMI, waist circumference
- Vital signs (heart rate, systolic and diastolic blood pressure at the right arm after at least 5 minutes at rest sitting)
- Questionnaires
 - Respiratory symptoms
 - Quality of life
 - Physical activity
 - Anxiety
 - Depression
 - Sleep quality
 - Alcohol and illegal drug use
 - Environmental pollution exposure
- Exhaled breath composition (CO, oxidative stress markers in a subset of participants)
- Blood collection (lipids, HbA1c (only for participants with diabetes) & creatinine, inflammatory biomarkers)
- Urine collection (nicotine metabolites, VOCs, PAHs, nitrosamines, oxidative stress markers)
- Randomization to study group
- Distribution and instruction of ENDS and e-liquids (intervention group only)
- Smoking cessation counselling

- Scheduling of phone calls
- Pulmonary function tests (conventional and MBW in a subset of participants)
- Micronuclei assessment in buccal epithelium
- Olfactory function: Burghart Sniffin' Sticks 16-Item Identification Test
- Inflammatory biomarkers
- .

9.3.3 Phone calls at target quit date, week 1, week 2, week 4, and week 8

Phone calls at target quit date (corresponding to day 0) and after 1 week (± 2 days), 2 weeks (± 3 days), 4 weeks (± 4 days), and 8 weeks (± 1 week):

- Smoking status: cigarettes / ENDS
- Assessment of smoking cessation medication use: NRT, proven effective drug therapies (varenicline, bupropion) and other interventions without demonstrated efficacy (e.g. acupuncture, hypnose, sophrology etc)
- Assessment of AEs, ENDS deficiencies
- Smoking cessation counselling
- ENDS technical trouble shooting
- Scheduling of phone calls and outcome visit

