11.2 Determination of Sample Size

Primary outcome:

Sample size calculation of the ESTxENDS trial at 6 months follow-up: Based on the results of a systematic review and meta-analysis of previous trials, we expect an RR of smoking cessation of 1.6. Based on our previous RCTs, we expect a 12% quit rate in the control group and a 19% quit rate in the intervention group (ENDS + SOC) (7% absolute difference in continuous abstinence rate from target quit date [TQD]) for the main outcome in ESTxENDS at 6 months. With a two-sided alpha of 0.05 and a power of 90%, we therefore planned to include a minimum 557 smokers per group, for a total of 1,114 smokers, to find a significant difference in quit rates. Previous experience suggests we should assume a 5% loss to follow-up, so we increased our sample size by 5% (59 smokers). We will thus recruit 1,172 smokers. Though participants in the control group will not be actively provided with ENDS and asked not to use ENDS during the first 6 months of the study, we expect that 5% will still purchase ENDS on their own. The sample size of the entire trial is based on the primary outcome; the power to find a statistically significant difference for secondary outcomes is limited to the total number of participants.

Estimated power to detect significant differences in groups on smoking cessation at 12- and 24-months follow-up: Assuming 10% will have quit smoking in the control group at 12 months (continuous smoking cessation rate from TQD), and applying the RR of 1.6, we estimate 16% will have quit in the intervention group. Assuming 7% loss to follow-up, we will have 86% power to detect such a difference. Based on the literature and previous experience in our own trials,^{133, 163} we expect a 10% relative increase in absolute smoking cessation rate by choosing 7-days point prevalence as the main outcome with no change in RR estimate.¹⁶³ We will have 90% power to detect a significant difference by choosing the 7-days point prevalence as a main outcome for the 12-months follow-up. We thus expect an 11% quit rate in the control group and 17% in the intervention group at the 12-month follow-up (6% absolute difference). At the 24-month follow-up, we can expect 8% in the control group will have stopped smoking and 12% in the intervention group. Assuming a 10% loss to follow-up rate, we will have 62% power to detect a significant difference between groups.

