11.4.2 Primary Analysis

To answer the primary research question, we will compare the rates of quitting among smokers randomized to ENDS vs. those receiving usual care, on an intention-to-treat basis. Continuous smoking cessation from target quit date will be the main outcome, confirmed by biomarkers of exposure (anabasine). We will calculate quit rates, relative risks (RR), and absolute risks for ENDS +SOC (intervention group) compared to SOC alone (control group). We will further compare groups using multivariate regression models adjusting for appropriate co-variates. Participants who stopped smoking, and who are continuous ENDS users, will be considered quitters.

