2.2 Randomization

Simple randomization in a 1:1 ratio to the two arms.

CTU Bern	SAP for: ESTxENDS	Version: 1-02.0	
CTU Bern	Template: Statistical Analysis Plan (SAP)	Version: 03	
	Code: CS_STA_TEM-11	Valid from: 28-02-2019 to 06.2023	Page 6 of 27

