6.5 Missing data

Missing values in the primary outcome will be categorized as persistent smokers. We intend to obtain full follow-up data on all randomized participants.

Missing data in secondary smoking cessation outcomes will be treated as the primary outcome. If more than 5% of data is missing, all other secondary outcomes will be imputed, assuming values to be missing at random. Each outcome will be imputed separately to ensure robust imputation models. We will use all baseline variables (see Table 2) and outcome measures at all time points as predictors in the imputation models. The two intervention groups will be imputed separately. Variables with more than 50% missing values will not be used for the imputation model. Binary variables with a frequency of less than 5% in one category will be omitted from the predictors, levels of categorical variables with a frequency of less than 5% in one category will be combined with another level in a sensible way. Continuous variables will be log-transformed if it improves normality (checked by Shapiro-Wilks test and QQ plots). If predictors are too highly correlated among each other, we will only consider the predictor which is more strongly correlated with the outcome. In case of missing baseline covariates, ~~W~~we will use multiple imputation by chained equation. We will impute values using predictive mean matching for continuous and ordinal variables, logistic regression for binary variables, and a multinomial regression model for categorical variables with more than two levels. In total, fifty imputed data sets will be generated, which will be analysed as described using Rubin's rules (Rubin 1987). We will compute stabilized inverse probability of censoring weights to take into account potentially informative censoring or outcome data.

CTU Bern	SAP for: ESTxENDS	Version: 4.02.0
----------	-------------------	------------------------

CTU Bern	Template: Statistical Analysis Plan (SAP)	Version: 03
	Code: CS_STA_TEM-11	Valid from: 28.02.2019 5.6.2023

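### The primary analysis is a valid but unadjusted chi-square; the adjusted model that the protocol promises is left unspecified, and dependence score and site appear in no named model or in SAP Table 2

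*Supplement*

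**What the plan says.** **Primary comparison.** SAP 2.0 section 6.3.1 gives the quit proportion per arm with a Wilson interval, "compared between groups using the chi-square test". The effect sizes are a relative risk (Koopman interval) and a risk difference (Newcombe interval). No covariate enters. Section 6.3.3 adds an available-case analysis, and sections 6.3.4 and 6.3.5 plan nothing more by the trials unit.

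**Adjusted models.** Protocol 9.0 section 11.4.2 says of the same comparison: "We will further compare groups using multivariate regression models adjusting for appropriate co-variates". It names no covariate. Section 11.5 puts censoring weights inside these regression models as a sensitivity analysis and names no predictors for them.

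**Allocation.** SAP section 2.2: "Simple randomization in a 1:1 ratio to the two arms". Five sites recruit, and no stratification factor is listed.

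**Baseline data.** Protocol section 9.3.2 collects "Smoking history and symptoms linked to smoking, cigarette dependence", the latter by the Fagerström test. SAP Table 2 lists demography, medical history, respiratory and asthma scores, the Minnesota withdrawal scale, anabasine and NNAL. It has no row for the Fagerström score, cigarettes per day or site.

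**Missing data.** SAP section 6.5 counts a missing cessation outcome as smoking. For the other secondary outcomes: "We will use all baseline variables (see Table 2) and outcome measures at all time points as predictors in the imputation models". SAP 2.0 adds stabilised inverse-probability-of-censoring weights without naming their predictors.

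**Who analyses.** SAP section 7, Table 4, says the study team, aware of allocation, took over all analyses.

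**The concern.** In a cessation trial, dependence and daily consumption are natural candidates for predicting who quits, and site may matter too. Simple randomisation balances them only on average, so a chance difference stays in an unadjusted estimate, and the outcome variance that they explain stays in its standard error. An adjusted estimate recovers some of that precision from data already collected.

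Its value depends on the covariates being fixed beforehand. Here the protocol leaves them open and the SAP does not fill the gap, while the analysts can see allocation. The same applies to the weights. The history of changes to the protocol records selective withdrawal in the control group, and weights correct for informative dropout only if their model holds what drives both dropout and outcome.

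**Working it through.** **1. The plan's own figure.** Protocol section 11.2: "With a two-sided alpha of 0.05 and a power of 90%, we therefore planned to include a minimum 557 smokers per group", for quit rates of 12% and 19%. The unpooled two-proportion formula gives

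n = (1.960 + 1.282)² × (0.12 × 0.88 + 0.19 × 0.81) / 0.07² = 10.507 × 0.2595 / 0.0049 = 556.4, so 557 per arm.

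This matches exactly; the pooled version gives 560. The planned 90% power therefore rests on an unadjusted comparison and needs no covariates.

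**2. Unadjusted power at the number analysed.** Missing cessation outcomes count as smoking, so all 586 per arm stay in the analysis. Taking 12% and 19% as the rates under that rule:

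- pooled SE = √(2 × 0.155 × 0.845 / 586) = 0.02114
- unpooled SE = √(0.2595 / 586) = 0.02104
- power = Φ((0.07 − 1.96 × 0.02114) / 0.02104) = Φ(1.357) = 91.3%.

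**3. Gain from adjustment.** The documents give no prognostic strength, so R² (the share of outcome variance explained by baseline covariates) is an assumption, shown over a range. Effective n is 586 / (1 − R²). The half-width of the risk-difference interval is 1.96 × 0.02104 × √(1 − R²).

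| R² | Effective n per arm | Power | 95% half-width (points) | n per arm for 90% power |
|---|---|---|---|---|
| 0 | 586 | 91.3% | 4.12 | 560 |
| 0.02 | 598 | 91.8% | 4.08 | 549 |
| 0.05 | 617 | 92.6% | 4.02 | 532 |
| 0.10 | 651 | 93.8% | 3.91 | 504 |

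The gain is about 0.5 to 2.5 points of power, with an interval 1% to 5% narrower.

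**4. Which part of the range is plausible.** A simulation (2,000 runs per setting, 586 per arm, one normal baseline covariate) with odds ratios of 1.3, 1.5 and 2.0 per SD gave R² of about 0.01, 0.02 and 0.06. Logistic adjustment changed power by +0.3, +0.2 and +1.0 points, with a simulation error of about 0.6 points on each power estimate. The lower half of the table is therefore the more likely one.

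**5. Validity and chance imbalance.** In the same simulation the unadjusted test had a type I error of 4.8% to 5.3%. Under simple randomisation a given covariate differs between arms by more than 0.1 SD with probability 2 × (1 − Φ(0.1 / √(2/586))) = 0.087. With an odds ratio of 1.5 per SD (assumption), such a difference moves a quit rate by about 0.1 × ln 1.5 × p(1 − p): 0.4 points at 12% and 0.6 points at 19%, against a planned difference of 7 points. The test's error rate and the interval already allow for this.

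**6. Where each predictor enters.**

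- *Cigarettes per day:* not in Table 2. SAP section 6.1 lists it as an outcome measured at baseline, so it enters the imputation through the outcome-measures clause of section 6.5.
- *Fagerström score:* not in Table 2 and not an outcome in SAP section 6.1, so neither clause brings it in.
- *Site:* not in Table 2 and in no named model. SAP section 3.2 uses centre only for data checks.
- *Adjusted model of the primary outcome:* protocol section 11.4 leaves the models to the SAP, while SAP section 7 leaves further analyses to the protocol and does not specify them. The one covariate that the protocol does name, use of cessation medication during the trial (section 8.7), arises after randomisation.
- *Censoring weights:* predictors named in neither document. The closing note on SAP changes says that these weights replaced chained-equation imputation, so their predictors matter the more.

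**The case against.** The strongest reply is that nothing is broken. The chi-square is valid under simple, unstratified 1:1 randomisation, the trial was sized for it, and chance imbalance is part of its error rate. All of that stands.

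A second reply is that adjustment is already planned in protocol section 11.4.2, and that SAP section 6.3.5 says only that the trials unit will do no more. This stands in part: an adjusted analysis is promised. But a promise without covariates prespecifies nothing, and the people who would now choose them know the allocation.

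A reader might infer that the collected baseline predictors help neither the estimate nor the missing-data models. The documents do not support that. Table 2 already carries anabasine, NNAL and the withdrawal scale into the imputation, and baseline cigarettes per day enters as an outcome measure. Nor does imputation without dependence distort the quit rates: missing cessation outcomes are set to smoking and are never imputed. The recorded control-arm attrition therefore bears on the weighted analyses and the other secondary outcomes, not on the primary chi-square.

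**Conclusion.** The point holds as one of efficiency and prespecification. The primary estimate is unadjusted, the promised adjusted model has no named covariates, the predictors of the censoring weights are open, and dependence score and site appear in no named model or in the baseline table. As listed, Table 2 would not show whether the arms were equally dependent or smoked equally at entry.

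The size is modest: from 91.3% to about 91.8% to 93.8% power at 586 per arm for an assumed R² of 0.02 to 0.10, probably near the lower end. This rests on the plan's 12% and 19% quit rates and on R², which the documents do not give. It does not show bias, an inflated type I error or an underpowered trial.

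**What to change.** 1. In SAP section 6.3.1 keep the chi-square and its intervals. Add one prespecified adjusted estimate: a logistic model with arm, site, baseline dependence score and baseline cigarettes per day, standardised to a marginal relative risk and risk difference with robust 95% confidence intervals. Refer to it from protocol section 11.4.2.
2. In SAP section 6.5 name the predictors of the censoring weights and include the same baseline covariates.
3. Add dependence score, cigarettes per day and site to SAP Table 2, so that they are reported by arm and enter the imputation models wherever these are used.

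The cost is a few lines of SAP text and code. The data are already collected, and neither the sample size nor the primary test changes.

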6.3.2 Secondary analyses

Secondary analyses are based on the principal strata estimand, using the per-protocol analysis set. Binary outcomes will be presented as proportion with 95% Wilson confidence interval in each intervention group and compared between groups using the chi-square test. Effect sizes will be presented as relative risk with 95% Koopman confidence interval, as well as risk difference with 95% Newcombe-hybrid-score confidence interval. Continuous outcomes will be analysed using linear models, adjusted for outcome measures at baseline, if available, with mean differences (95% confidence interval) as effect sizes. If secondary outcomes are missing, we will use the imputed datasets generated for the primary analysis.

6.3.3 Sensitivity analyses

As sensitivity analysis, we will do an available case analysis of the primary outcome, using the full analysis patient set. No further sensitivity analyses will be performed by CTU Bern.

CTU Bern	SAP for: ESTxENDS	Version: 1.02.0	
CTU Bern	Template: Statistical Analysis Plan (SAP)	Version: 03	
	Code: CS_STA_TEM-11	Valid from: 28.02.2019 to 06.2023	Page 23 of 27

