INTERVENTION										
ENDS & e-liquid distribution		E								
E-liquid order by participants				E	E	E	E	E		
E-liquid sent to their homes					E	E	E	E		
ENDS instruction		E								
ENDS technical support			E	E	E	E	E	E		
Structured smoking cessation counselling		x	x	x	x	x	x	x	x	x
OUTCOME MARKERS										
Tobacco use (questionnaires)	x	x	x	x	x	x	x	X*	X*	X*
Estimated ENDS use (ml e-liquids used)			E	E	E	E	E	E*	E*	E*
Exhaled CO		x						x	x	x
Urinary nicotine, cotinine, anabasine		x						x	x	x
Urinary metabolites of nitrosamines (TSNAs)		x						x	x	x

Procedure	Screening ①	Baseline visit	Day 0 ①	Week 1 ①	Week 2 ①	Week 4 ①	Week 8 ①	Outcome Visit Month 6	Outcome visit Month 12	Outcome visit Month 24
Adverse events, serious AE			x	x	x	x	x	X*	X*	X*
VOC and PAH metabolites in urine		x						x	x	x
Oxidative stress markers in urine		x						x	x	x
Oxidative stress in exhaled breath (Lausanne site only)		x						x		
Blood pressure, heart rate, height, weight (BMI), waist circumference		x						x	x	x
Blood lipids, HbA1c (only for participants with diabetes), creat.		x						x	x	x
Respiratory symptoms		x						X*	X*	X*
Pulmonary function test parameters (FEV1, FVC, FEV1/FVC, PEF, FEF25-75%, TLC, FRC, RV/TLC, DLCO) (Bern site only)		x						x	x	x
Multiple breath washout (MBW) parameters (LCI, Scond, Sacin) (Bern site only)		x						x	x	x
Parameters of ventilation, perfusion and structural changes of the lung (MRI; Bern site only)+								x		
Micronuclei frequency (micronuclei assessment)		x						x	x	x
Olfactory function parameters (odor identification score (OIS))		x						x	x	x
"Dry-hit" recognition								E		
Inflammatory biomarkers		x						x		

E: ENDS group only; C: Control group only

* possibility of having participants fill the questionnaire online

+ A aged matched group of healthy never smoking/non-vaping volunteers (N=10) will perform once two consecutive MRI measurements. These volunteers are not participants of the RCT.

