October 10 th , 2019 / November 26 th 2019	Approval of changes: 
 1. Study site Zürich (Nov 26th) and St-Gallen (Oct 10th). 2. Extension of follow-up to 12- and 24-months. 3. Vouchers to control group given at baseline instead of giving them the voucher after completion of the 6-months visit. 4. Adaptations of documentation of Adverse Events 	Protocol version 7.0, Dated September 10 th , 2019. 
 1. Extension of recruitment to study site Zürich and St-Gallen to meet recruitment targets. 2. Additional funding obtained by Tobacco Prevention Fund and Swiss Cancer Research enabling extension of follow-up to 12- and 24-months follow-up 3. We noticed selective attrition through withdrawal in the control group. We decided the control group should receive a voucher at baseline instead of 6-months follow-up to mitigate deception in control group. 4. Further adaptations in documentation of AE by study nurses with systematic queries to hospitals and attending physicians in case of AE and not only SAE
October 11 th , 2019	Information to CEC related to EVALI epidemic in USA: 
 1. Letter sent to all participants asking them to report any respiratory symptoms 	
 1. In light of the reports in the USA about EVALI cases, the research team reviewed already collected SAE and AE, reviewed the literature and reports coming out of the USA and decided to pursue the study as planned. We sent a letter to participants informing them about the situation in the USA, which was most likely due to use of illicit e-liquids or e-liquids used for vaping cannabis and that they should continue to report adverse events to study nurses. 2.
March 2020, until July 2020	Incremental lockdown measures related to COVID pandemic decided by Federal Council of Switzerland. 
 1. Pause in recruitment of new participants from: March to July 2020 2. Shift as much as possible clinical follow-up visit from in-person visits to phone follow-ups. 	
 1. COVID pandemic required us to pause recruitment of new participants. 2. Study nurses continued to follow-up participants at scheduled times over the phone, following up participants in person if allowed locally.

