6.1 Outcome definitions

Primary outcome: The primary outcome will be the continuous cigarette smoking abstinence from target quit date to the 6-month follow-up visit, ascertained by self-report at the 6-month follow-up exam (self-report of no smoking from target quit date) and confirmed by urinary level of anabasine (<3 ng/ml). If anabasine is missing, validation by exhaled carbon monoxide (CO). The outcome is a binary outcome.

Core secondary outcomes:

- Secondary smoking cessation outcomes to the 6-month follow-up visit:
 - Continuous smoking abstinence. Self-report of having smoked no cigarettes from TQD, validated by urinary levels of NNAL (4-(methylnitrosamino)-1-(3-pyridyl)-1-butanol). If NNAL is missing, validation by urinary levels of anabasine or exhaled CO.
 - Self-reported smoking abstinence allowing a 2-week 'grace period' after the TQD
 - Validated smoking abstinence allowing a 2-week 'grace period' after the TQD, validated by urinary levels of anabasine. If anabasine is missing validation by exhaled CO.
 - Validated smoking abstinence allowing a 2-week 'grace period' after the TQD, validated by urinary levels of NNAL. If NNAL is missing, validation by urinary levels of anabasine or exhaled CO.
 - Self-reported smoking abstinence allowing up to 5 cigarettes in total after the TQD.
 - Validated smoking abstinence allowing up to 5 cigarettes in total after the TQD, validated by urinary levels of anabasine. If anabasine is missing validation by exhaled CO.
 - Validated smoking abstinence allowing up to 5 cigarettes in total after the TQD, validated by urinary levels of NNAL. If NNAL is missing, validation by urinary levels of anabasine or exhaled carbon monoxide (CO).
 - Self-reported 7-day point prevalence abstinence at 6 months, Self-report of having smoked no cigarettes in the past seven days.
 - Validated 7-day point prevalence abstinence. Confirmation of having smoked no cigarettes in the past seven days, validated by urinary levels of anabasine. If anabasine is missing validation by exhaled carbon monoxide (CO).
 - Validated 7-day point prevalence abstinence. Confirmation of having smoked no cigarettes in the past seven days, validated by urinary levels of NNAL. If NNAL is missing, validation by urinary levels of anabasine or exhaled carbon monoxide (CO).

CTU Bern	SAP for: ESTxENDS	Version: 4.02.0	
CTU Bern	Template: Statistical Analysis Plan (SAP)	Version: 03	
	Code: CS_STA_TEM-11	Valid from: 28.02.2019 to 06.2023	Page 18 of 27

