6.2 Derivation of Outcomes

Comments to secondary smoking cessation outcomes:

- Smoking is allowed during the grace period.
- The number of cigarettes smoked since the last visit is recorded as a categorical variable (1-5 cigarettes, >5 cigarettes). If the participant smoked more than once a day cigarettes in the last 7 days, the value is recorded as numeric variable. For secondary smoking cessation outcomes, we will assume the median value for the categorical variable. I.e. if a subject records 2 times to smoke 1-5 cigarettes, we assume him to be over the limit of 5 cigarettes.

Table 3: Derivation of primary and secondary outcomes.

Outcome	eCRF sheet	Variable	Variable type	Derivation	Outcome type
Primary: continuous smoking abstinence from target quit date to the 6-month follow-up visit AND	cig_ecig	quit_smoke_again	Binary: No, Yes	{ [Week 1/2/4/8, and month 6] quit_smoke_again == No AND quit_tobacco_inhale ==	Binary
		quit_tobacco_inhale	Binary: No, Yes		
	cig_ecig_6m	quit_smoke_again	Binary: No, Yes		
		quit_tobacco_inhale	Binary: No, Yes		

CTU Bern	SAP for: ESTxENDS	Version: 1-02.0
-----------------	-------------------	---------------------------------

CTU Bern	Template: Statistical Analysis Plan (SAP)	Version: 03
	Code: CS_STA_TEM-11	Valid from: 28-02-2019 to 05-06-2023

urinary level of anabasine (<3 ng/ml) OR	to be defined	to be defined	to be defined	No} AND {x < 3 if x!=missing, vs_co2_level<10 if x==missing & vs_co2_level ==missing}
CO level	vital_6m	vs_co2_level	Continuous	
Secondary outcomes				
continuous smoking abstinence from target quit date to the 6-month follow-up visit AND	Cig_ecig, cig_ecig_6m	quit_smoke_again, quit_tobacco_inhale	Binary: No, Yes, Binary:No, Yes	{[Week 1/2/4/8, and month 6] quit_smoke_again == No AND quit_tobacco_inhale == No} AND
urinary level of NNAL (<10 pg/ml creat) OR	To be defined	To be defined	To be defined	{y < 10 if y!=missing, x<3 if y==missing & x!=missing, vs_co2_level<10 if y==missing & x==miss- ing & vs_co2_level!=missing }
urinary level of anabasine (<3 ng/ml) OR	To be defined	To be defined	To be defined	
CO level	Vital, Vital_6m	vs_co2_level	continuous	
Continuous smoke abstinence allowing a 2-week grace period after TQD	cig_ecig / cig_ecig_6m	quit_smoke_again quit_tobacco_inhale	Binary: No, Yes	[Week 4, Week 8, and 6 months] sum(quit_smoke_again == No) >= 2 AND sum(quit_tobacco_in- hale == No) >= 2

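### Without a 6-month sample, a reported smoker is an observed failure but a reported abstainer is missing, so the available-case and weighted analyses should define availability by the sample, not by the answer

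*Supplement*

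**What the plan says.** SAP 2.0, section 6.1, defines the primary outcome as self-reported continuous abstinence from the target quit date, "confirmed by urinary level of anabasine (<3 ng/ml). If anabasine is missing, validation by exhaled carbon monoxide (CO"). Table 3 in section 6.2 joins the self-report part and the marker part with AND. Neither place says what happens when both markers are absent.

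Section 6.5 states: "Missing values in the primary outcome will be categorized as persistent smokers". Section 6.3.3 adds: "we will do an available case analysis of the primary outcome, using the full analysis patient set". It does not define *available*. Section 6.5 also announces stabilised inverse probability of censoring weights, without saying who counts as censored or which variables enter the weight model. Protocol 9.0, section 11.5, plans such weights as sensitivity analyses for missing main and secondary outcomes.

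The history of changes after protocol 9.0 records for March to July 2020: "Shift as much as possible clinical follow-up visit from in-person visits to phone follow-ups". The comment beside it reads: "Study nurses continued to follow-up participants at scheduled times over the phone, following up participants in person if allowed locally". In the study schedule of protocol 9.0, month-6 tobacco use carries a star for the "possibility of having participants fill the questionnaire online"; exhaled CO and urinary anabasine carry no star.

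**The concern.** A phone contact removes the marker and its back-up together. Because of the AND, the two possible answers then lead to different data states. Reported smoking settles the outcome without a sample; reported abstinence leaves it open.

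A lockdown is largely unrelated to whether a given person smokes, so losing samples to it would be fairly harmless if everyone without a sample were handled alike. Handling people by their answer turns a calendar-driven gap into missingness that depends on the outcome. The analyses meant to test the missing-equals-smoker rule would then share its direction of error and give false reassurance. A weight model built on baseline variables alone cannot repair this.

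**Working it through.** **1. The plan's own figure.** Protocol 9.0, section 11.2, assumes 12% v 19%, two-sided alpha 0.05 and 90% power, and states 557 per group. Unpooled formula: (1.960 + 1.282)² × (0.12×0.88 + 0.19×0.81) / 0.07² = 10.51 × 0.2595 / 0.0049, which rounds up to 557. It reproduces (pooled formula: 560). With 586 per arm, power is 91%.

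**2. How Table 3 classifies a 6-month contact.**

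| Sample at 6 months | Reports smoking | Reports abstinence |
|---|---|---|
| Anabasine or CO present | failure | decided by the marker |
| Neither present | failure | undetermined |

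The lower right cell becomes a smoker in the primary analysis. It drops out of an analysis of non-missing outcomes, while the lower left cell stays in.

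**3. Formulas.** Let p be the true abstinence rate and f the share of 6-month contacts without a sample. Assume that f is unrelated to smoking status and that self-reports are true. People never reached are left out, since they are missing on any rule.

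- Primary analysis: p(1−f)
- Available case, ordinary sense: p(1−f) / (1−fp), which is below p for any f above 0
- Available defined by the sample: p(1−f) / (1−f) = p

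**4. Numbers.** The documents do not give f; the values below are assumptions, the same in both arms.

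| f | Primary, control v ENDS (difference) | Available case, ordinary sense (difference; RR) | Defined by sample (difference; RR) |
|---|---|---|---|
| 5% | 11.4% v 18.1% (6.7) | 11.5% v 18.2% (6.8; 1.59) | 12% v 19% (7.0; 1.58) |
| 10% | 10.8% v 17.1% (6.3) | 10.9% v 17.4% (6.5; 1.59) | 12% v 19% (7.0; 1.58) |
| 20% | 9.6% v 15.2% (5.6) | 9.8% v 15.8% (6.0; 1.61) | 12% v 19% (7.0; 1.58) |
| 30% | 8.4% v 13.3% (4.9) | 8.7% v 14.1% (5.4; 1.62) | 12% v 19% (7.0; 1.58) |

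Example at f = 20%, ENDS arm: 0.19×0.80 / (1 − 0.20×0.19) = 0.152 / 0.962 = 15.8%. About 14 control and 22 ENDS abstainers would be dropped (586×0.20×0.12 and 586×0.20×0.19). The available-case analysis recovers only a small part of what the primary rule removes.

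**5. Unequal shares, for illustration only.** With f = 10% in the ENDS arm and 20% in control, the primary RR is 0.171/0.096 = 1.78 and the available-case RR 1.77. Reversed, they are 1.41 and 1.45. The direction is therefore open, and the available-case result follows the primary one.

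**The case against.** The strongest reply is that *available case* is undefined. If it means self-report and marker both present, sample-less smokers drop out too and the asymmetry disappears. Table 3 allows a third reading, because it ties the CO check to CO being absent ("vs_co2_level<10 if x==missing & vs_co2_level ==missing"). That looks like a slip against section 6.1, but coded literally it could keep sample-less abstainers in as failures. This stands: the finding depends on the ordinary meaning of the term. On no reading, though, does a sample-less abstainer count as abstinent, and the three readings give different results.

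A reader might infer that this is the only sensitivity analysis of the primary outcome. It is not: protocol 11.5 and SAP 6.5 add censoring weights, and section 6.3.3 limits only what the trials unit does. Weights that condition on the reported answer could even undo the problem, but no weight model is given.

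A reader might also infer that nothing shows what validation removes. Section 6.1 pairs self-reported with validated versions of the grace-period, up-to-5-cigarette and 7-day outcomes, which show part of it. The pair for continuous abstinence is absent, and the existing pairs mix people who failed a marker with people who never had one.

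Nor were samples necessarily lost for everyone in those months. In-person visits continued where allowed, the window runs from day 152 to day 264, and the online questionnaire does not cancel the scheduled CO and urine.

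Finally, phone reports of smoking are real information, some of it from the week 1 to 8 calls, and setting it aside has a cost. That is fair, and the fix keeps it in a companion analysis.

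**Conclusion.** The point holds for the sensitivity analyses. Under section 6.1 and Table 3, a contact without urine or CO gives a known failure or an unknown outcome according to the answer. The available-case analysis in its ordinary sense, and the weights if censored means lacking a validated outcome, then understate quit rates and the risk difference in both arms.

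The size is unknown. At an assumed 10% to 20% without a sample in both arms, the difference is 6.5 to 6.0 points against 7.0. The 7.0 presumes that phone-reported abstinence is true, which is what validation exists to test. The RR hardly moves.

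A stronger reading would be that the RR is distorted because in-person attendance differed by arm. The documents do not show that. The control-arm withdrawal they record is listed with protocol 7.0 of September 2019. It predates the pandemic, concerns people who withdrew rather than people reached by phone, and was answered by moving the voucher to baseline. Nor is the primary rule itself a fault: coding missing as smoking is declared and conservative.

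**What to change.** 1. In SAP 6.3.3 and 6.5, define *available* and *censored* by whether a 6-month anabasine or CO result exists, whatever answer was given. Put visit mode or calendar period in the weight model. Calendar period is safer if phone contacts never gave a sample, since mode would then determine censoring completely. As a companion, show the result with failures already established by self-report kept in.
2. Add self-reported continuous abstinence from the target quit date to section 6.1 and Table 3 as a secondary outcome, shown by arm and by whether a sample was obtained.

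Keep the present rule as the primary analysis. Collecting samples late is no longer an option: protocol 9.0 planned the last participant out for 05/22, and SAP 2.0 is dated June 2023.

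The cost is SAP wording and two small extra analyses on data already collected. The available-case analysis also loses the sample-less reported smokers. At f = 10%, it goes from about 579 control and 575 ENDS participants (586×(1−fp)) to about 527 in each arm (586×0.90).
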